16.3 EFFICACY ANALYSIS

16.3.1 Baseline characteristics

Frequency analyses will be used to produce descriptive statistics of the sample as regards demographic, anthropogenic, clinical, or other characteristics (gender, age, race, weight, height, smoking habits, etc.)

16.3.2 Primary endpoint

The **primary endpoint** of the study regards the accuracy of SpO₂ and HR measurements of BrOxy M. The *accuracy* of the experimental BrOxy M will be evaluated by comparing SpO₂ readings of the BrOxy M to the values obtained with the secondary standard pulse oximeter equipment (Nellcor™ Bedside Respiratory Patient Monitoring System model PM1000N, Covidien LLC, USA), that is traceable to co-oximeter SaO₂ values.

The following routines will be used:

- The paired t test, to evaluate the differences between experimental and standard values: the paired sample *t*-test procedure determines whether the mean difference between two sets of observations is zero. It regards *pairs* of observations.
- Correlation analysis, to quantify the degree to which experimental and standard values are related: it is a bivariate analysis that measures the strength of the association between two variables. The degree of association is measured by a correlation coefficient (r) on a scale that varies from + 1 through 0 to 1. We expect a positive correlation: r>0.70 indicate a strong correlation, and r=1 a perfect correlation.
- Concordance correlation coefficient (CCC), to evaluate whether the experimental value is interchangeable with the standard; this statistic quantifies the agreement between a new measurement and a gold standard measurement. Also CCC varies from -1 to 1, with perfect agreement at 1.
- Bland -Altman (B&A) plot, to evaluate the agreement between experimental and standard values; the B&A plot analysis is a simple way to evaluate a bias between the mean differences, and to estimate an agreement interval, within which 95% of the differences of the second method, compared to the first one, fall. Data can be analyzed both as unit differences plot and as percentage differences. The Bland-Altman chart is a scatterplot with the difference of the two measurements for each sample on the vertical axis and the average of the two measurements on the horizontal axis. Three horizontal reference lines are superimposed on the scatterplot one line at the average difference between the measurements, along with lines to mark the upper and lower control limits of plus and minus 1.96*the standard deviation of the measurement differences. Bland and Altman also discuss the option of using confidence interval bounds, based on the standard error of the mean, for the upper and lower reference lines. If the two methods are comparable, then differences should be small, with the mean of the differences close to 0, and show no systematic variation with the mean of the two measurements. 'Small' would be an amount that would be clinically insignificant for the factor being measured.

Clinical Investigational Plan			
Protocol No.:	Version 1.0	Page 36 of 45	
01M2020-CH.LMD	Date: 22 December 2020		

• Linear regression analysis: to give further information about any potential proportional bias about the mean differences and averages. It is a simple test for a linear trend, with the mean difference as dependent variable and the average difference as independent. The aim is to evaluate if the mean difference can be predicted from the average. The resulting coefficients indicate whether one can accept the null hypothesis that there is no proportional bias.

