 SpO₂ and HR values corresponding to the same time points selected for the reference device will
 be chosen.

Clinical Investigational Plan		
Protocol No.:	Version 1.0	Page 16 of 45
01M2020-CH.LMD	Date: 22 December 2020	1 486 10 01 13

As a result, it is expected that from each enrolled subject up to 32 paired measurements of SpO_2 and HR will be obtained from the reference device and BrOxy M. Table 1 below summarises the data collection process.

Plateau no.	Range SpO₂ (%)	Inhaled solution	Plateau duration	No. of Measurements of SpO ₂ and HR extracted from recordings
1)	95 – 100 (target 97%)	Ambient air (medical air)	2.5'	8
II)	90 – 94 (target 92%)	O2 15% + N 85%	2.5'	8
III)	85 – 89 (target 87%)	O2 13% + N 87%	2.5'	8
IV)	80 – 84 (target 82%)	O2 11% +N 89%	2.5'	8
			Total	32 measurements

Table 1: Number of measurements to be performed for each subject, for each target level of SpO₂ and indication of the gaseous solution inhaled during each target level.

After completing the study on 10 subjects, collecting around 320 paired measurements it will be verified that, by dividing the desaturation interval into three equal parts, each part contains around a third of the measurements made. Therefore, considering the minimum target number of 200 measurements (per EN 80601-2-61 standard) and the interval between 98% and 82% of SaO_2 to be divided into three parts, at the end of the protocol on all the subjects recruited, it is expected to have:

- At least 67 measurements between 98% and 93% of SpO₂;
- At least 67 measurements between 92% and 87% of SpO₂;
- At least 67 measurements between 86% and 82% of SpO₂

In the event that this minimum target is not reached to meet the requirements of the EN 80601-2-61 standard, it may be necessary to recruit up to 2 additional subjects.

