7 OBJECTIVES AND ENDPOINTS

7.1 OBJECTIVES

The **primary objective** of the study is to confirm the performance of BrOxy M in comparison with a reference, CE marked, pulse oximeter equipment in a controlled desaturation study.

The **secondary objectives** of the study are:

- To assess BrOxy M performance in subjects with different skin pigmentation (Note: this is a tentative objective, since few subjects are planned to be enrolled and there is no guarantee that they will have different skin pigmentation)
- to confirm BrOxy M safety

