10 STUDY SUBJECTS

The study population will include adult healthy volunteers who will accept to participate in this oxygen desaturation study in a controlled clinical environment. At least 11 healthy subjects will be enrolled. Data collected on the first subject will not be used for accuracy measurements but will serve to finalize the test set up phase and ensure adequate recording procedures are used by site staff. On each of the remaining 10 subjects, 32 paired measurements will be performed in order to obtain a maximum of 320 "valid" measurements (see Section 17.2) which guarantees a statistically significant accuracy study (see point EE2.3.4 of the ISO 80601-2-61: 2017 standard).

To take into account invalid data and potential drop out samples up to 2 additional subjects may need to be enrolled. For this reason sample size for this study will be between a minimum of 11 and a maximum of 13 healthy volunteers.

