16 STATISTICAL ANALYSIS

16.1 OVERVIEW

Statistical analyses will be performed with SPSS, Statistical Package for the Social Sciences (SPSS Inc, Chicago, IL), by following the requirements of the standard ISO 80601-2-61:2017 ("Medical electrical equipment - Part 2-61: particular requirements for basic safety and essential performance of pulse oximeter equipment, Procedure for non-invasive laboratory testing on healthy adult volunteers).

The *significance level*, that is the probability of rejecting the null hypothesis when it is true, will be set to 0.05 (two-sided, corresponding 5% risk of concluding that a difference exists when there is no actual difference).

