16.2 ANALYSIS SETS

Analyses will regard 320 pair measurements (80 in the ambient air, and 80 for each of the four defined target levels, that will be obtained from 10 healthy subjects).

Clinical Investigational Plan			
Protocol No.:	Version 1.0	Dana 25 of 45	
01M2020-CH.LMD	Date: 22 December 2020	Page 35 of 45	

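### The paired t test of zero mean difference cannot confirm accuracy: it ignores scatter, its 5% level guards the other error, and no agreement routine has a limit that would decide instead

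*Combined protocol and SAP*

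**What the plan says.** The primary objective in Section 7.1 is to "confirm the performance of BrOxy M in comparison with a reference" pulse oximeter, and the primary endpoint is the accuracy of SpO2 and HR in paired readings. Section 16.3.2 lists five routines for it:

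- **Paired t test.** "The paired t test, to evaluate the differences between experimental and standard values"; the plan adds that the "procedure determines whether the mean difference between two sets of observations is zero".
- **Correlation.** r above 0.70 is called strong. This is the only numeric benchmark among the five.
- **Concordance correlation coefficient (CCC).** It is to judge whether the two devices are interchangeable. No acceptance value is given.
- **Bland-Altman plot.** It is to judge agreement, with limits at the mean difference plus or minus 1.96 SD. Differences should be small, which is described in words only.
- **Linear regression of the differences on the averages.** It looks for proportional bias, and the text speaks of whether the null can be accepted.

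Section 16.1 sets the significance level at 0.05 and explains it as "two-sided, corresponding 5% risk of concluding that a difference exists when there is no actual difference". Section 16.2 states: "Analyses will regard 320 pair measurements". The plan gives no margin, expected bias, SD of the differences or power, and no rule for which routine decides that performance is confirmed.

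**The concern.** In a confirmation study the costly error is to conclude that the device agrees when it does not. A test whose null is zero mean difference controls the opposite error. Random error in BrOxy M sits in the denominator of t, so for any non-zero bias a noisier device is less likely to be flagged. Positive and negative errors also cancel in the numerator. A precise device with a trivial offset can therefore show a significant difference while a much less precise one shows none. With no numeric limit on the other routines, a report could set a reassuring p-value beside wide limits of agreement, and nothing in the plan would settle how to read the two together.

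**Working it through.** **Inputs from the documents.** Section 10: "On each of the remaining 10 subjects, 32 paired measurements will be performed in order to obtain a maximum of 320" valid measurements, so 10 × 32 = 320, which reproduces the number in Section 16.2. Section 3 sets a minimum of 200. The level is 0.05 two-sided (16.1). The plateau targets are 97, 92, 87 and 82% (Table 1). The reference device's own error is ±2 digits for SpO2 (Section 6).

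**Assumptions.** The documents give neither bias nor SD of the differences, so both are shown over a range. Pairs are first taken as independent, as the plan's test does.

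**Chance of p>0.05.** The noncentrality is bias / (SD/√n), with √320 = 17.89 and critical value 1.967 on 319 degrees of freedom. For bias 0.5 this gives 0.5 × 17.89 / 2 = 4.47 at SD 2 and 0.5 × 17.89 / 4 = 2.24 at SD 4. The RMS difference is √(bias² + SD²).

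| Bias | SD | p>0.05, n=320 | p>0.05, n=200 | RMS difference | Limits of agreement |
|---|---|---|---|---|---|
| 0.5 | 1 | about 0% | about 0% | 1.12 | −1.46 to 2.46 |
| 0.5 | 2 | 0.6% | 6.0% | 2.06 | −3.42 to 4.42 |
| 0.5 | 3 | 15.6% | 35.0% | 3.04 | −5.38 to 6.38 |
| 0.5 | 4 | 39.4% | 57.9% | 4.03 | −7.34 to 8.34 |
| 0 | 1 to 4 | 95% | 95% | equal to SD | ±1.96 SD |

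With a non-zero bias, more noise means fewer rejections. With a bias of exactly zero the rate is 95% at every SD: the test then does not favour noise but is blind to it.

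**Smallest significant offset.** 1.967 × SD/17.89 gives 0.11 points at SD 1 and 0.22 at SD 2. Both are far inside the reference's own ±2 digits.

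**Does r>0.70 catch the noisy device?** Four equal plateaus have mean 89.5 and variance (7.5² + 2.5² + 2.5² + 7.5²)/4 = 31.25. At SD 4, r = √(31.25/(31.25 + 16)) = 0.81. Adding assumed reference variation (subject SD 0.7, reading SD 1) gives 0.82. The benchmark is met with limits of agreement of roughly ±8 points.

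**Does the direction depend on independence?** In a simulation of 10 subjects with 32 pairs each and bias 0.5, a test on subject means rejected in 99.7% of trials at between- and within-subject SDs of 0.25 and 0.97 (RMS 1.1). It rejected in 22% at SDs of 1 and 3.87 (RMS 4.0). The problem therefore remains after clustering is handled.

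**The case against.** The strongest reply is that the t test is one routine of five and is not the one assigned to agreement. CCC is named for interchangeability and Bland-Altman for agreement, and both count scatter. A mean bias near zero with wide limits is one coherent result, since the t test speaks to the centre line and the limits to the spread. This stands, and it is why the point is a recommendation rather than a fatal flaw. It would be a full answer if either routine had a numeric limit or were made decisive; neither is.

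A reader might go further than the documents allow in three ways.

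- **That the plan equates p>0.05 with agreement.** No sentence says so for the t test. The nearest wording concerns accepting the null for the regression slope, which shows a habit of reading non-significance as support but is not a decision rule.
- **That the t test is the only test of the differences.** The slope regression is another.
- **That a grossly inaccurate device would pass.** A device with a constant output would have a CCC of 0 and a slope rejected in every simulated trial. At SD 8, r is about 0.58, below the plan's own 0.70. The plan's other routines expose both.

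The moderate case does survive. At SD 4 the slope test rejects in every simulated trial if all readings are kept, but in only about 1% once readings outside 80 to 100% SpO2 are dropped, as Section 17.2 requires. After that filter the SD is about 3.6, r about 0.77, and the t test still gives p>0.05 in about 41% of trials.

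The analysis is also tied to an ISO standard that is not part of these documents, so the absence of a deciding rule is shown for this plan only.

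**Conclusion.** The concern holds. The first-listed routine for the primary endpoint tests a null that a confirmation study cannot use as evidence of accuracy, and the stated 5% level does not limit the risk of wrongly concluding agreement. On an assumed bias of 0.5 points and 320 independent pairs, doubling the SD from 2 to 4 raises the chance of a non-significant result from 0.6% to 39%. At the 200-reading minimum the corresponding figures are 6% and 58%. These figures rest on assumed bias and SD; the direction does not, provided the bias is not zero. The harm is partly contained by CCC and Bland-Altman. It is not removed, because they carry no limit and the one numeric benchmark is met by a device with limits of agreement of about ±8 points.

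**What to change.** In Section 16.3.2 replace the paired t test, for SpO2 and for HR separately, with:

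- (a) the mean difference with a two-sided 95% confidence interval computed on subject means;
- (b) the root-mean-square difference, √(mean d²), with an interval that respects clustering by subject, such as a bootstrap of subjects, reported beside the Bland-Altman limits.

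State that agreement is judged by these against a limit fixed before analysis, and that p>0.05 is not evidence of zero difference.

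The sponsor should justify the limit. The ±2 digits and ±3 bpm in Section 6 are the reference's own error and should not be adopted unexamined for the difference between two devices. For SpO2, if ±2 digits is one SD, an error-free BrOxy M would still show an RMS difference of about 2.0. If it is a 95% bound, the figure is 2/1.96, or about 1.0. Section 6 does not say which is meant, and the limit must allow for it.

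Keep the 0.05 level in Section 16.1, because the slope, ANOVA and logistic tests use it. Add that it does not control the risk of wrongly concluding agreement.

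The cost is SAP wording and a little more analysis, with no new data or subjects. The downside is that an agreement statement becomes harder to earn. With 10 subjects the half-width of interval (a) is 0.715 times the SD of the subject means (2.262/√10).

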In this context, albeit with a significantly lower prevalence than the aforementioned chronic diseases, but reported in widespread increase, idiopathic pulmonary fibrosis (IPF) also deserves to be mentioned. IPF causes a serious reduction in respiratory function and patient's health state, characterized by dyspnea following minimal physical strain, secondary to the development of marked respiratory insufficiency, and by rapid and progressive impairment of the state of health which leads to a very severe prognosis despite the currently available pharmacological treatments (30, 31).

Reliable measurement of oxygen saturation and heart rate are generally obtained at certain predetermined times and with the use of equipment that is not always easy to use, that is burdensome for the patient and is usually obtained in a hospital or outpatient setting, imposing a limitation in subject mobility and activity. There is currently no availability on the market of a non-invasive and easy to use instrument capable of providing the clinician with reliable measurements of oxygen saturation and heart rate recorded continuously both during the day, while the subject carries out his normal activities, and during the period of night sleep.

BrOxy M is a new, CE marked, pulse oximeter that is wearable like a watch and as such is not burdensome for the patient. BrOxy M is a medical device that can continuously record oxygen saturation and heart rate and, potentially, also other parameters during a 24-hour period, while the subject carries out his/her daily physical activity and even at night. This allows a more precise diagnosis and allows a more appropriate therapy with considerable advantages for the subject's health and quality of life and, at the same time, with a reduction in costs at the expense of the public health system.

STUDY DESIGN 3

The study is a post market clinical follow up study performed to confirm the performance of BrOxy M pulse oximeter in comparison with a reference, CE marked, pulse oximeter equipment (Nellcor™ Bedside Respiratory Patient Monitoring System model PM1000N, Covidien LLC, USA - from now on "reference device") in a controlled desaturation study.

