7.2 ENDPOINTS

The **primary endpoint** of the study will be a comparison of the accuracy of SpO_2 and HR measurements obtained with BrOxy M with that obtained with the reference pulse oximeter in paired observations over a range between 80% and 100% SpO_2 .

For each subject, four different saturation plateaus will be set up (i.e. at 97%, 92%, 87% and 82% SpO_2), waiting 30" before starting to keep the SpO_2 level on each plateau for 2.5' in order to obtain 8 measurements in post-processing. These measurements will be at least 20" away from each other, for a total of 32 measurements for each subject, as summarized in Table 1.

The study will follow the procedures described in the standard ISO 80601-2-61:2017 "Medical electrical equipment - Part 2-61: particular requirements for basic safety and essential performance of pulse oximeter equipment".

As **secondary endpoints**, the following will be verified:

• whether any relation exists between the accuracy of BrOxy M for both SpO₂ and HR and subject skin pigmentations as measured with the Fitzpatrick scale.

Clinical Investigational Plan			
Protocol No.:	Version 1.0	Page 22 of 45	
01M2020-CH.LMD	Date: 22 December 2020	1.80 == 0. 10	

• that no adverse events related to the use of BrOxy M, besides a temporary slight skin irritation of the wrist, will occur.

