15.2 ANTICIPATED ADVERSE EVENTS

AEs that have been identified as risks through the risk management process and therefore can be considered as "anticipated" for the purposes of this study are:

- temporary slight skin irritation of the wrist related to the use of BrOXy M
- temporary transitory non critical increase of the heart rate and blood pressure
- mild hyperventilation

It is expected that the above symptoms will be resolved in few minutes (<5 minutes) after the interruption/completion of the test session.

Clinical Investigational Plan			
Protocol No.:	Version 1.0	Page 34 of 45	
01M2020-CH.LMD	Date: 22 December 2020	rage 34 01 43	

Refer to Section 8.2 RISKS for further details.

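### For heart rate, the pooled correlation and CCC ignore the subject, so when volunteers differ in rate at least as much as each varies, they largely reflect level differences and can look good without within-person tracking

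*Combined protocol and SAP*

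**What the plan says.** The primary endpoint in Section 7.2 covers SpO2 and HR. For HR it compares "HR measurements obtained with BrOxy M with that obtained with the reference pulse oximeter in paired observations". Each volunteer contributes many readings, "for a total of 32 measurements for each subject", and Section 16.2 pools them: "Analyses will regard 320 pair measurements", "that will be obtained from 10 healthy subjects".

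Section 16.3.2 lists five routines. Two concern us here. The first is a correlation: "it is a bivariate analysis that measures the strength of the association between two variables". A value above 0.70 is described as strong. The second is "Concordance correlation coefficient (CCC), to evaluate whether the experimental value is interchangeable with the standard"; the section gives its scale but no cut-off. The others are a paired t test, a Bland-Altman plot and a regression of the difference on the average.

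Sections 16.1 to 16.3.3 contain no subject term, repeated-measures model or within-person statistic. The only stratification, in 16.3.3, is by skin pigmentation. Section 15.2 anticipates a "temporary transitory non critical increase of the heart rate and blood pressure" but gives no size, and no between-person or within-person SD of HR appears anywhere.

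**The concern.** The gas mixtures move every volunteer's SpO2 through four planned levels. Nothing does that for HR. Its spread across the 320 pairs combines differences in level between 10 people with whatever change occurs within each person, and a pooled r or CCC does not separate the two. A device that merely distinguishes a volunteer with a slow heart from one with a fast heart can score well on both.

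The purpose described in the Introduction depends on following one wearer over time: "BrOxy M is a medical device that can continuously record oxygen saturation and heart rate". If r and CCC are quoted as the HR result, they can support a statement about HR performance that the data do not bear out. This is not a standard-error problem. Correcting the precision of the pooled r for clustering would leave its value, and the question it answers, unchanged.

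**Working it through.** **Inputs from the plan.** 10 analysed subjects, 4 plateaus, 8 readings per plateau, and the 0.70 label. Check: 10 × 4 × 8 = 320, the figure in 16.2. (That section's wording, read literally, gives 80 + 4 × 80 = 400; 320 requires ambient air to be one of the four plateaus, as in Table 1.)

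**Inputs assumed, because the documents give none.** Person mean around 75 bpm with between-person SD 6, 8, 10 or 12; a four-step mean rise of 8 or 15 bpm, each person's share of it having mean 1 and SD 0.3; within-plateau SD 3; non-tracking device = person's session mean plus noise of SD 2; accurate device = reference plus noise of SD 1.5.

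**Closed form.** Let B and W be the between-person and within-person variances of HR, and ICC = B/(B + W). For a device frozen at each person's mean, ignoring its noise, the covariance with the reference is B, so r = B/√(B(B + W)) = √ICC and CCC = 2B/(2B + W) = 2·ICC/(1 + ICC).

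| Between SD / within SD | r | CCC |
|---|---|---|
| 0.5 | 0.45 | 0.33 |
| 1.0 | 0.71 | 0.67 |
| 1.5 | 0.83 | 0.82 |
| 2.0 | 0.89 | 0.89 |

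r passes 0.70 once ICC > 0.49, that is, once the SD ratio exceeds √(0.49/0.51) = 0.98.

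**Where the assumptions fall.** Four equal steps from 0 to 1 have variance 5/36, and the person's share has mean square 1 + 0.3² = 1.09.
- 8 bpm rise: W = 64 × 5/36 × 1.09 + 9 = 18.7, SD 4.3.
- 15 bpm rise: W = 225 × 5/36 × 1.09 + 9 = 43.1, SD 6.6.

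Between-person SDs of 8 to 12 lie above the threshold in both cases. SD 6 with a 15 bpm rise lies below it (6/6.6 = 0.91).

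**Simulation of the non-tracking device.**

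| Rise | Between SD | Mean pooled r | r > 0.70 |
|---|---|---|---|
| 8 | 8 / 10 / 12 | 0.82 / 0.87 / 0.91 | about 93% / 98% / over 99% |
| 15 | 8 to 12 | 0.72 to 0.84 | about 64% to 95% |
| 8 | 6 | – | about 70% |
| 15 | 6 | – | about 25% |

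For the 8 bpm rows at SD 8 / 10 / 12, mean CCC is 0.82 / 0.87 / 0.90. Within-person r is 0.00 throughout and never exceeds 0.70.

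A second simulation (SD 6 to 12, rise 5 to 20 bpm, 16 combinations) put median r above 0.70 in 13 of 16 for a device frozen at the session mean and in 10 of 16 for one frozen at the resting value. The between-person share of variance ran from about 36% to 90%.

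**The other planned routines.**
- Bland-Altman half-width: about 9 bpm (8 bpm rise) or 13 bpm (15 bpm rise), against 1.96 × 1.5 = 2.9 for the accurate device.
- Regression slope: significant in about 75% to 100% of trials for the session-mean device, but also in about 18% to 47% for the accurate one.
- Paired t test: never flags the session-mean device; essentially always flags the resting-value device.

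**Does a within-person r treat a good device fairly?** With no reference error the accurate device scores 0.945 to 0.975. Section 6 gives the reference an HR error of 3 bpm either way. Taking that as an error SD of 1.5 bpm for both devices (an assumption), r = W/(W + 2.25). For a 3 bpm rise the step variance is 9 × 5/36 × 1.09 = 1.36. Within-plateau SD 1.5 gives 3.61/5.86 = 0.62, and SD 2 gives 5.36/7.61 = 0.70. In simulation such a device exceeds 0.70 in only about 1% to 60% of trials.

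**The case against.** A reader might infer that the plan would declare a non-tracking device interchangeable. It would not. The CCC has no cut-off, and 0.70 is a descriptive label, not an acceptance criterion. Equally, no written rule would prevent that reading.

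A reader might also infer that pooled HR statistics always mainly reflect differences between people. The documents give no HR variances, and with a small spread between volunteers and a large rise the between-person share falls below half.

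The strongest objection is that the plan already contains routines that expose the failure: wide limits of agreement and a sloping regression. That largely stands. Its limits are that the regression also fires often for a good device, and that 16.3.2 describes an acceptable difference only as clinically unimportant, with no HR figure. The session-mean device is also artificial, since it needs future readings. The more natural device frozen at rest is caught by the t test, and its CCC fell as low as 0.25 in the second simulation.

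Finally, the comparison sentence in 16.3.2 mentions only SpO2 readings, so applying the routines to HR is inferred from the endpoint. If they were not meant for HR, HR would have no primary analysis, so the section needs an edit either way.

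**Conclusion.** The point holds conditionally. When the between-person SD of HR is about equal to or above the within-person SD, pooled r and CCC say little about whether the device follows a wearer's HR, and the plan has no statistic that addresses this directly. The sizes above rest on assumed variances: at SD 8 to 12 and a rise of 8 to 15 bpm, a device with no tracking usually earns the strong label; at SD 6 and 15 bpm it usually does not. The misleading picture arises if r and CCC are read without the Bland-Altman and regression results. This merits a change to the analysis text; it does not invalidate the study.

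**What to change.** In 16.3.2, state that the routines apply to HR and, beside the pooled HR values, add:
- the within-subject (repeated-measures) correlation, with a confidence interval from resampling subjects;
- a repeated-measures CCC with its within-subject and between-subject parts shown separately;
- the within-subject SD of reference HR and the within-subject root-mean-square difference in bpm.

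Base any statement on HR tracking on these. Do not attach the strong label to the pooled HR r, and do not move 0.70 across as a cut-off for the within-subject r: a small HR excursion plus reference error can pull an accurate device below it.

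The cost is plan wording and a few lines of analysis on data already to be collected, with no added subjects or procedures. The downside is that the HR result will look less favourable than the pooled one, and will be imprecise if HR hardly changes during the session.

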The following routines will be used: the paired t test, to evaluate the differences between experimental and standard values; correlation analysis, to quantify the degree to which experimental and standard values are related; concordance correlation coefficient (CCC), to evaluate whether the experimental value is interchangeable with the standard; Bland -Altman (B&A) plot, to evaluate the agreement between experimental and standard values; linear regression analysis to give further information about any potential proportional bias about the mean differences and averages.

^{*} ECG required at screening unless a 12-lead ECG has been performed in the last 2 months prior to screening

^{**}pregnancy test only for pre-menopausal women.

Protocol No.: Version 1.0

01M2020-CH.LMD Date: 22 December 2020

Page 13 of 45

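### Section 16.3.2 names no deciding accuracy statistic and writes down no acceptable SpO2 or HR error; if a limit from ISO 80601-2-61:2017 is intended, it has not been transcribed

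*Combined protocol and SAP*

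**What the plan says.** Section 7.1 states the primary objective as confirming performance against the reference oximeter. Section 7.2 defines the primary endpoint as a comparison of SpO2 and HR accuracy and attaches no limit.

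Section 16.3.2 then lists five routines without ranking them:

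- **Paired t test.** The "procedure determines whether the mean difference between two sets of observations is zero". Section 16.1 sets alpha at 0.05 two-sided, glossed as a "5% risk of concluding that a difference exists when there is no actual difference".
- **Correlation.** "We expect a positive correlation: r>0.70 indicate a strong correlation, and r=1 a perfect correlation".
- **CCC.** The synopsis gives its purpose: "concordance correlation coefficient (CCC), to evaluate whether the experimental value is interchangeable with the standard". The scale is described, but there is no cut-off.
- **Bland-Altman.** The limits are ±1.96 SD of the observed differences. A small difference "would be an amount that would be clinically insignificant for the factor being measured"; no number follows for SpO2 or HR.
- **Regression of difference on average.** The coefficients are to show whether "one can accept the null hypothesis that there is no proportional bias".

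Section 16.1 says the analyses are done "by following the requirements of the standard ISO 80601-2-61:2017". It gives no accuracy limit and no clause for one. The only error figures in the documents, ±2 digits for SpO2 and ±3 bpm for HR in Section 6, are the specification of the reference device.

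**The concern.** A study that confirms performance needs a stated quantity and a stated limit. Here the documents supply neither, and the two numeric benchmarks answer other questions. The t test asks whether the mean difference is exactly zero. The correlation asks whether the two devices move together across a range that the protocol itself makes wide. The slope test is worded so that non-significance supports the absence of proportional bias, which it does not. CCC and Bland-Altman do show the size of disagreement, but have no limit to be judged against.

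The five results can point in different directions on the same data, and the documents contain no rule for that case, nor one for combining SpO2 with HR. Unless the standard supplies the criterion, whether performance is confirmed is settled after ten results (five routines, two parameters) are known.

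**Working it through.** The documents give no SD, bias, ICC or margin. All values of these below are assumptions.

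**Plan's own count.** 10 subjects × 4 plateaus × 8 readings = 320 pairs, 80 per plateau. This reproduces the 320 in Section 16.2.

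**1. How much error does r > 0.70 allow?** Plateau targets (Section 3, Table 1) are 97, 92, 87 and 82, with mean 89.5. Variance = (7.5² + 2.5² + 2.5² + 7.5²)/4 = 31.25, so SD = 5.59. With a within-plateau SD of 1, s = √(31.25 + 1) = 5.68. For independent error of SD e, r = s/√(s² + e²), so r = 0.70 at e = s·√(1/0.49 − 1) = 1.0202·s.

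- SpO2: e = 1.0202 × 5.68 = 5.79; limits ±1.96 × 5.79 = ±11.4. (Within-plateau SD 0.5 to 1.5 gives e = 5.73 to 5.90.)
- HR: the tolerated error SD is 1.02 times the spread of HR itself, whatever that is.
- A constant bias does not change r. Using the targets alone (s² = 31.25) and e = 2, r = 5.59/√(31.25 + 4) = 0.94 whether bias is 0 or 4. RMS goes from 2.0 to √(4 + 16) = 4.5, and CCC from 62.5/66.5 = 0.94 to 62.5/82.5 = 0.76.

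**2. The same with the 80–100% window (Section 17.2).** Simulation: 10 × 4 × 8 pairs, reference ~ N(target, 1), device = reference + error, pairs dropped if either value lies outside 80–100.

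| Error SD | r | Limits of agreement | Observed RMS |
|---|---|---|---|
| 4.65 | 0.70 | ±8.0 | 4.1 |
| 4.0 | 0.77 | ±7.0 | 3.6 |

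At SD 4 about 270 of 320 pairs remain and CCC is 0.77. The filter on BrOxy M readings removes the largest errors near the ends of the range, so a true RMS of 4.0 appears as about 3.6.

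**3. Accurate device, pooled t test.** Bias 0.3, SD 1.5: SE = 1.5/√320 = 0.0839, critical difference 1.967 × 0.0839 = 0.165. Independent pairs: non-centrality 0.3/0.0839 = 3.58, probability of significance 0.946. With within-subject ICC ρ, the true SE is 0.0839·√(1 + 31ρ):

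- ρ = 0.1: 0.170, probability about 0.79
- ρ = 0.5: 0.341, probability about 0.74

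Simulation agrees; across runs the range is roughly 73–95%. The limits of agreement are only 1.96 × 1.5 = ±2.9 around the bias.

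**4. Bound for RMS.** One option is a MOVER-type bound. With subject means m_j of n_j differences and N pairs in all, let A = Σn_j·m_j²/N and W = within-subject sum of squares/N. Then U = A + W + √{[A(10/χ²₀.₀₅,₁₀ − 1)]² + [W((N−10)/χ²₀.₀₅,N₋₁₀ − 1)]²}, and the one-sided 95% bound is √U.

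- With pairs selected on the reference reading only, coverage was about 95–98% (ICC 0.1–0.5). Ignoring clustering gave 66–93%.
- With the filter also applied to BrOxy M, coverage of a true RMS of 4.0 fell to about 42–84%.
- With RMS 2.0 and bias 0.5, the bound is below 2.5 in 37–70% of studies and below 3.0 in 78–99% (ICC 0.5 to 0.2).
- With RMS 2.0 and bias 1.5 it is conservative: coverage 0.99–1.00, below 2.5 in only about 7–14% and below 3.0 in 54–87% (ICC 0.1–0.5).

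**5. Reference error.** If the reference has independent error of SD 1 to 2 points, a device RMS of 2.0 appears as √(4 + 1) = 2.2 to √(4 + 4) = 2.8.

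**The case against.** **The standard may supply the limit.** Several sections say the study follows ISO 80601-2-61:2017, and Section 16.1 ties its requirements to the statistical analyses. If the standard sets an accuracy statistic and limit, the gap is one of transcription. This stands: a reader might infer that there is no criterion at all and that confirmation is pure judgement, but the documents do not support going that far, because they cannot show what the standard contains. They do show that the plan is specific when it relies on the standard elsewhere: a minimum of 200 measurements (Section 3), EE.3 for the reference device (Section 6) and EE2.3.4 for the measurement count (Section 10). For acceptable error there is neither number nor clause.

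**The endpoint is a comparison, not a test of equivalence.** The five routines have different stated purposes, and different answers to different questions need not conflict. This is fair for reporting them all. It does not meet an objective worded as confirmation.

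**The benchmarks are not pass rules.** Correct. A reader might infer that a non-significant t test, r above 0.70 and a non-significant slope together would count as success. The plan says no such thing; r > 0.70 is an expectation and a label, and CCC and Bland-Altman would display a large error in the same report.

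**Some of the remedy is preference.** This also stands for the choice of bound, whether the bound or the point estimate decides, and any requirement that SpO2 and HR both pass. If the standard uses a point estimate, a bound would be an added hurdle.

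**Conclusion.** The concern holds in this form: the documents name no deciding statistic and write down no acceptable error for SpO2 or HR, and any limit meant to come from the standard is not transcribed or cited. That part rests on the text alone.

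The size of the problem rests on assumed SDs, biases and ICCs. Under them, the r benchmark tolerates SpO2 limits of agreement of about ±11 points (±8 with the window), while a zero-difference test can flag a device whose limits are about ±3. The plateau spread of 5.6 points follows from the protocol's own targets, so the weakness of r does not depend much on the assumptions. No numeric limit is proposed here, because the documents give no basis for one.

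**What to change.** In Section 16.3.2:

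1. Name the RMS paired difference, √(mean d²), as the deciding accuracy statistic: points for SpO2, bpm for HR. It combines bias and spread.
2. Have the sponsor write one numeric limit per parameter before data are processed. Cite the clause if it comes from the standard, and say whether the limit allows for the reference's own error (±2 digits, ±3 bpm).
3. Report RMS with a confidence bound that accounts for clustering within the 10 subjects; MOVER is optional. Whether the estimate or the bound decides should follow the cited standard or be stated by the sponsor.
4. Compute SpO2 RMS on pairs whose reference SpO2 is 80–100%, whatever BrOxy M reads, or report it both ways. Report the number of pairs removed by the HR 40–280 check.
5. Keep bias, Bland-Altman limits and CCC as supporting results. Make the t test, r and slope descriptive. Delete the r > 0.70 benchmark and the wording about accepting the null hypothesis.

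The cost is SAP wording, one computed statistic and keeping BrOxy M values calculated before the range check; no further measurements. The downside is that the sponsor commits in advance, and with 10 subjects a limit close to the true RMS may not be met, especially for a biased device if the bound decides.
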